## 7.6.7 Immune Modulating Medication

Immune modulating concomitant medications are medications entered on an immune modulating medication form or available from the most current pre-defined list of immune modulating medications. The list of anatomic class, therapeutic class and generic name used for the selection at the time of the database lock will be provided.

The percentage of subjects who received immune modulating concomitant medication for

- management of adverse event
- premedication
- other use
- any use
- management of drug-related select adverse event (any grade, grade 3-5) by select AE category/subcategory (EU/ROW Submissions)
- management of IMAEs (any grade, grade 3-5) by IMAE category (US Submission) will be reported separately for each treatment group (percentages of treated subjects by medication class and generic term).

For each category/subcategory of drug-related select AEs (any grade, grade 3-5) and IMAEs (any grade, grade 3-5), the following will be reported for each treatment group:

• The total immune modulating medication treatment duration (excluding overlaps), duration of high dose of corticosteroid, initial dose of corticosteroid, and tapering duration (summary statistics)

Duration represents the total duration the subject received the concomitant medication of interest. If the subject took the medication periodically, then DURATION in the summation of all use. Initial dose represents the dose of the concomitant medication of interest received at the start of the event. In the case multiple medications started on the same date, the highest equivalent dose is chosen and converted to mg/kg by dividing by the subject's recent weight.

These analyses, except the ones related to IMAEs will be conducted using the 30-day safety window. The analyses related to IMAEs will be conducted using the 100-day safety window.

## 7.6.8 Multiple Events

The following summary tables will be provided:

- A table showing the total number and rate (exposure adjusted) of occurrences for all AEs.
- A table showing the total number and rate (exposure adjusted) of occurrences for AEs occurring in at least 5% of subjects in any treatment group.

In addition, the rate (exposure adjusted) and its 95% CI evaluated for different time intervals will be displayed graphically for each treatment group. This analysis will be limited to the rate of all AEs and all drug-related AEs. The analyses will be conducted using the 30-day safety window.

A listing displaying the unique instances of all AEs, i.e., after duplicates have been eliminated and overlapping and contiguous occurrences of the same event (i.e. same PT) have been collapsed will be provided. No formal comparisons will be made between treatment groups.

#### 7.6.9 Other Events of Special Interest

OEOSI will be summarized by treatment group for each category.

The following analyses will be conducted using the 100-day safety window:

- Overall summary of OEOSI by worst CTC grade (any grade, grade 3-4, grade 5) presented by Category / PT
- Overall summary of drug-related OEOSI by worst CTC grade (any grade, grade 3-4, grade 5) presented by Category / PT

A by-subject listing of OEOSI will be provided.

#### 7.6.10 Immune Mediated Adverse Events

IMAEs will be summarized by treatment group for each immune-mediated category / PT using the 100-day safety window:

- Overall summary of non-endocrine IMAEs by worst CTC grade (any grade, grade 3-4, grade 5) where immune modulating medication was initiated presented by Category / PT.
- Overall summary of endocrine IMAEs by worst CTC grade (any grade, grade 3-4, grade 5) presented by Category / PT.
- Overall summary of non-endocrine IMAEs leading to discontinuation by worst CTC grade (any grade, grade 3-4, grade 5) where immune modulating medication was initiated presented by Category / PT.
- Overall summary of endocrine IMAEs leading to discontinuation by worst CTC grade (any grade, grade 3-4, grade 5) presented by Category / PT.

- Overall summary of non-endocrine IMAEs leading to dose delay or reduction by worst CTC grade (any grade, grade 3-4, grade 5) where immune modulating medication was initiated presented by Category / PT
- Overall summary of endocrine IMAEs leading to dose delay or reduction by worst CTC grade (any grade, grade 3-4, grade 5) presented by Category / PT.
- Summaries of time-to onset and time-to resolution of non-endocrine IMAEs where immune modulating medication was initiated presented by Category.
- Summaries of time-to onset and time-to resolution of endocrine IMAEs presented by Category.

A by-subject listing of IMAEs will be provided. By-subject listings of time-to resolution for longest IMAEs cluster (any grade and grade 3-5 in separate summaries) will also be provided. For new studies which collect investigator assessment of potential IMAE data, a by-subject listing of AEs considered as immune-mediated events per investigator but not qualified for IMAEs definition will also be provided.

In addition, for all Nivolumab and/or Ipilimumab treated subjects who experienced at least one IMAE, the following data presentation will be provided:

• Summary of subjects who were re-challenged with Nivolumab and/or Ipilimumab by IMAE category, with extended follow-up

For these, re-challenge is considered to have occurred when last Nivolumab and/or Ipilimumab infusion was administered after the onset of an IMAE.

## 7.6.11 Clinical Laboratory Evaluations

The analysis population for each laboratory test is restricted to treated subjects who underwent that laboratory test. Laboratory tests (in addition to the tests specified below) with CTC criteria collected in the specific studies may also be included in the summaries.

A by-subject listing of differences in categorization of SI and US laboratory test results will be provided.

## **7.6.11.1** Hematology

The following will be summarized by treatment group as worst CTC grade on-treatment per subject and as shift table of worst on-treatment CTC grade compared to baseline CTC grade per subject: hemoglobin (HB), platelets, white blood counts (WBC), absolute neutrophils count (ANC) and lymphocyte count (LYMPH).

The analyses will be conducted using the 30-day safety window.

A by-subject listing of these laboratory parameters will be provided.

#### 7.6.11.2 Serum Chemistry

The following will be summarized by treatment group as worst CTC grade on-treatment per subject and as shift table of worst on-treatment CTC grade compared to baseline CTC grade per subject: ALT, AST, alkaline phosphatase (ALP), total bilirubin and creatinine.

The analyses will be conducted using the 30-day safety window.

A by-subject listing of these laboratory parameters will be provided.

#### 7.6.11.3 Electrolytes

The following will be summarized by treatment group as worst CTC grade on-treatment per subject and as shift table of worst on-treatment CTC grade compared to baseline CTC grade per subject: sodium (high and low), potassium (high and low), calcium (high and low), and Glucose Serum.

The analyses will be conducted using the 30-day safety window.

A by-subject listing of these laboratory parameters will be provided.

## 7.6.11.4 Additional Analyses

In addition, further analyses on specific laboratory parameters will be performed by treatment group:

#### **Abnormal Hepatic Function Test**

The number of subjects with the following laboratory abnormalities from on-treatment evaluations will be summarized by treatment group:

- ALT or AST > 3 x ULN, > 5 x ULN, > 10 x ULN and > 20 x ULN
- Total bilirubin > 2 x ULN
- ALP  $> 1.5 \times ULN$
- Concurrent (within 1 day) ALT or AST > 3 x ULN and total bilirubin > 1.5 x ULN
- Concurrent (within 30 days) ALT or AST > 3 x ULN and total bilirubin > 1.5 x ULN
- Concurrent (within 1 day) ALT or AST > 3 x ULN and total bilirubin > 2 x ULN
- Concurrent (within 30 days) ALT or AST > 3 x ULN and total bilirubin > 2 x ULN

The analyses will be conducted using the 30-day safety window.

A by-subject listing of these specific abnormalities will be provided.

#### Abnormal Thyroid Function Test

The number of subjects with the following laboratory abnormalities from on-treatment evaluations will be summarized by treatment group:

- TSH value > ULN and
  - with baseline TSH value ≤ ULN

- with at least one FT3/FT4 test value < LLN within 2-week window after the abnormal TSH test

- with all FT3/FT4 test values ≥ LLN within 2-week window after the abnormal TSH test
- with FT3/FT4 missing within 2-week window after the abnormal TSH test.

#### TSH < LLN and

- with baseline TSH value ≥ LLN
- with at least one FT3/FT4 test value > ULN within 2-week window after the abnormal TSH test
- with all FT3/FT4 test values ≤ ULN within 2-week window after the abnormal TSH test
- with FT3/FT4 missing within 2-week window after the abnormal TSH test

The analyses will be conducted using the 30-day safety window.

A by-subject listing of these specific abnormalities will be provided.

#### 7.6.12 Vital Signs

Vital signs collected on the CRF will be provided in separate listings.

## 7.6.13 Immunogenicity Analysis

Nivolumab-containing arms only. Further details on immunogenicity background and rationale, definitions, population for analyses and endpoints are described in APPENDIX 4.

#### 7.6.14 Pregnancy

A by-subject listing of pregnancy tests results will be provided for randomized female subjects.

#### 7.6.15 Adverse Events by Subgroup

Overall summary of any AEs and drug-related AEs by worst CTC grade (any grade, grade 3-4, grade 5) presented by SOC/PT and for each treatment group for the following subgroups:

- Sex (Male vs. Female)
- Race (Asian vs. non-Asian)
- Age ( $< 65 \text{ vs. } 65 \text{ -} < 75 \text{ vs. } 75 \text{ -} < 85 \text{ vs. } \ge 85 \text{ vs. } \ge 75 \text{ vs. } \ge 65$ )
- Region (J/K/T vs rest of Asia vs RoW)

These analyses will be conducted using the 30-day safety window only.

## 7.7 Pharmacokinetic Analysis

Pharmacokinetics analyses will be performed on the nivolumab-containing arms only.

The nivolumab and/or ipilimumab concentration vs time data obtained in this study may be combined with data from other studies in the clinical development program to develop population PK models. These models may be used to evaluate the effects of intrinsic and extrinsic covariates

on the PK of nivolumab and/or ipilimumab and to determine measures of individual exposure (such as steady state peak, trough and time averaged concentration). Model determined exposures may be used for exposure response analyses of selected efficacy and safety endpoints. If the analyses are conducted, the results of population PK and exposure response analyses will be reported separately.

## 7.8 Biomarker Analysis

These analyses will be descriptive and not adjusted for multiplicity.

#### 7.8.1 PD-L1 Expression

Analyses will be performed in all randomized subjects, by treatment group as randomized.

## 7.8.1.1 Distribution of PD-L1 Expression

Descriptive statistics of PD-L1 expression and PD-L1 status will be provided;

- Summary statistics of PD-L1 expression by treatment groups as randomized and overall
- Frequency of PD-L1 categorization: PD-L1 status (1%, 5% and 10%) by treatment group and overall, all randomized PD-L1 subjects

## 7.8.1.2 Association between PD-L1 Status and Efficacy

Analyses will be based on all PD-L1 randomized subjects if not otherwise specified. PD-L1 status categories (1%, 5% and 10%) will be used for these analyses.

For both OS and PFS per BICR, the following analyses will be provided:

- Within each category above, curves will be estimated using the KM product limit method for each treatment group. Two-sided, 95% CIs for median OS and PFS per BICR will be computed by Brookmeyer and Crowley method.
- Two-sided log-rank test comparing treatment arms
- HR (with corresponding two-sided 95% CI) will be estimated via a Cox model with treatment arm as the only covariate in the model (note that for PDL1-expressing subjects, this is one of the sensitivity analyses, and won't be repeated; see Section 7.5.2.2)
- Forest plot of HR with 95% CIs
- For ORR per BICR, the following analyses will be provided:
- Within each category above, ORR per BICR will be computed in each treatment group along with the exact 95% CI using Clopper-Pearson method.
- An estimate of the difference in ORRs per BICR and corresponding 95% CI will be calculated using CMH methodology.

## 7.8.1.3 Predictive Relationship between PD-L1 Status and Efficacy

Analyses will be based on all evaluable PD-L1 subjects.

For both OS and PFS per BICR, a Cox proportional hazards regression model will be fitted with treatment, PD-L1 status, and treatment by PD-L1 status interaction. Although the study is not designed to have appropriate power to formally test the interaction of the model, an interaction test at significance level of 0.2 will warrant further exploration and the following statistics will be reported:

- Interaction p-value
- HR of treatment vs. control and its associated 95% CI for each of the PD-L1 status subgroup
- HR PD-L1  $\geq$  1% vs.  $\leq$  1% and its associated 95% CI within each treatment group.

# 7.8.2 PD-L1 by Combined positive score (CPS) and Microsatellite Instability (MSI) Status

Upon data availability, analyses of exploratory biomarker PD-L1 by CPS and MSI status will be performed in all randomized subjects, by treatment group as randomized.

#### 7.8.2.1 Descriptive Statistics of PD-L1 by CPS and MSI

- Summary of tumor specimen acquisition, characteristics by CPS and MSI respectively
- Summary of PD- L1 by CPS and MSI status by categories by CPS and MSI respectively Below analyses are applicable for PD-L1 by CPS
- Summary statistics of PD-L1 by CPS expression.
- Waterfall plot of Individual PD-L1 by CPS expression.

#### 7.8.2.2 Association between biomarker Status and Efficacy

OS and PFS per BICR will be analyzed for each biomarker category specified for PD-L1 by CPS and MSI:

- Curves will be estimated using the KM product limit method for each treatment group. Two-sided, 95% CIs for median PFS per BICR and OS will be computed.
- HR (with corresponding two-sided 95% CI) will be estimated via a Cox model with treatment arm as the only covariate in the model.
- Forest plot of HR with 95% CIs

## 7.9 Outcomes Research Analyses

The analysis of EQ-5D-3L and FACT-E (including FACT-G7 and ECS) data will be performed in all randomized subjects and all PD-L1 expressing subjects who have an assessment at baseline (assessment on or prior to first dose on Day 1) and at least 1 subsequent assessment while on treatment. The questionnaire completion rate, defined as the proportion of questionnaires actually received out of the expected number, will be calculated and summarized at each assessment point.

EQ-5D-3L data will be described by treatment group as randomized in the following ways:

- EQ-5D-3L index scores will be summarized at each assessment time point using descriptive statistics (i.e., N, mean with SD and 95% CI, median, first and third quartiles, minimum, maximum). The UK scoring algorithm will be applied as a reference case.
- EQ-VAS scores will be summarized at each assessment time point using descriptive statistics (i.e., N, mean with SD and 95% CI, median, first and third quartiles, minimum, maximum).
- The proportion (N) of subjects reporting no, moderate, or extreme problems will be presented for each of the 5 EQ-5D-3L dimensions at each assessment time point. Subjects with missing data will be excluded from the analysis.
- A line graph summarizing the mean changes from baseline for the EQ-5D-3L index and VAS scores will be produced.
- A by-subject listing of the level of problems in each dimension, corresponding EQ-5D-3L health state (i.e., 5-digit vector), EQ-5D-3L index score, and EQ-VAS score will be provided.

From the beginning of the on-treatment phase through follow-up Visit 2, data for the FACT-E will be described by treatment group as randomized in the following ways:

- FACT-G7 and FACT-E total and subscale (PWB, FWB, EWB, SWB, ECS, TOI) scores will be summarized at each assessment time point using descriptive statistics (i.e., N, mean with SD and 95% CI, median, first and third quartiles, minimum, maximum).
- Changes from baseline in FACT-G7, FACT-E total and subscale (PWB, FWB, EWB, SWB, ECS, TOI) scores will be summarized at each post-baseline assessment time point using descriptive statistics (i.e., N, mean with SD and 95% CI, median, first and third quartiles.
- The proportion (N) of subjects reporting each response category will be presented for the single-item GP5 item at each assessment time point. A stacked bar graph will be produced for GP5 which shows the proportion of subject with each response category at each timepoint. Subjects with missing data will be excluded from the analysis.
- A line graph summarizing the mean changes from baseline for the FACT-E total score, ECS and FACT-G7 scores will be produced.
- A by-subject listing of the responses to each item in the FACT-E will be provided (including the items also included in the ECS and FACT-G7 during the survival follow-up phase).

During the survival follow-up phase, data for the ECS and FACT-G7 will be described by treatment group as randomized in the following ways:

- ECS and FACT-G7 scores will be summarized at each assessment time point using descriptive statistics (i.e., N, mean with SD and 95% CI, median, first and third quartiles, minimum, maximum).
- Changes from baseline in ECS and FACT-G7 scores will be summarized at each post-baseline assessment time point using descriptive statistics (i.e., N, mean with SD and 95% CI, median, first and third quartiles, minimum, maximum).

#### 7.10 COVID-19 Related Analyses

In this study, in order to evaluate the impact of COVID-19 pandemic, the following CRF pages were implemented.

- Disposition: The subjects who discontinue the study treatment or discontinue the study due to COVID-19
- Exposure: The subjects who have study therapy modification due to COVID-19

Listings will be provided based on the data collected on each CRF pages and additional analyses may be performed in order to evaluate the impact of COVID-19 on this study.

# 8 Analysis to Evaluate the Contribution of Ipilimumab Component in the N+I regimen in the Summary of Clinical Efficacy (SCE)

In order to evaluate the treatment effect between two experiment arms of N+I and N+C, similar analyses as described in Section 7.5 will be conducted for key efficacy endpoints. The below analyses will be conducted for all PD-L1 expressing subjects, all PD-L1 Negative Subjects, and all Randomized Subjects. These analyses will help to evaluate the contribution of ipilimumab component in the N+I regimen in the Summary of Clinical Efficacy (SCE) and Clinical Overview (CO) if applicable.

For Overall survival and PFS as assessed by BICR, the HR between N+I and N+C with its associated two-sided 95% CIs will be estimated via a stratified Cox model with treatment arm as the only covariate in the model. Overall survival and PFS as assessed by BICR for each of the three treatment arms will be estimated and overlayed using the KM product-limit method. Median survival time along with 95% CI will be constructed based on a log-log transformed CI for the survival function.

ORR assessed by BICR will be computed in each treatment group along with the exact 95% CI using Clopper-Pearson method. An estimate of the difference in ORRs and corresponding 95% CI between N+I and N+C will be calculated using CMH methodology and adjusted by the stratification factors as specified in Section 7.1.1. The stratified odds ratios (Mantel-Haenszel estimator) between N+I and N+C will be provided along with the 95% CI. The KM curves of the DOR in each of 3 treatment groups will be overlayed for subjects who achieve PR or CR. Median DOR along with two-sided 95% CI will be calculated.

Considering that the survival function of overall survival may potentially have different shapes in the N+I arm and N+C arm, the restricted mean survival time (RMST) will be evaluated for N+I and N+C arm. The difference of RMST between N+I and N+C with its associated two-sided 95% CIs will be estimated. The RMST will be estimated by the area under the KM curve up to a time point (1 year, 2 years, and 3 years, and maximum of the study follow-up).

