### **1.1.3 Previous Studies of Nivolumab in Esophageal Cancer**

ONO-4538-07, a Phase 2, multi-center, open-label, single-arm study of nivolumab monotherapy 3 mg/kg IV every 2 weeks (Q2W) was conducted in subjects with esophageal cancer refractory or intolerant to standard therapies. The primary endpoint was ORR (immune-related response criteria (IRRC) assessed according to response evaluation criteria in solid tumors RECIST 1.1). Other secondary endpoints were ORR (investigator's assessment), OS, PFS, DCR, time to progression (TTP), time to response (TTR), best overall response (BOR), immune-related ORR (ir-ORR), ir-PFS, ir-DCR, duration of response (DOR), percent change from baseline in the sum of tumor diameters, and response of the primary esophageal lesion. The data included in this document is as of 17-May-2015; OS data as of 17-Nov-2015. This trial is being conducted at investigational sites in Japan.

A total of 65 subjects were enrolled and treated with nivolumab monotherapy. The median age was 62 years and around 70% of the subjects had 3 or more prior treatment regimens such as fluoropyrimidine, platinum, and taxanes (docetaxel or paclitaxel). Histological tumor type in all the subjects was squamous cell carcinoma. 54% of patients (21/37) expressed PD-L1 above the expression level of 1%.

Preliminary safety data demonstrated that the majority of subjects (84.6%) experienced an AE but most were Grade 1/2. Grade 3/4 AEs/SAEs occurred in 19% of patients and included: diarrhea, dysphagia, fatigue, liver function abnormal, lung infection, pneumonia and decreased appetite. The most frequent drug-related SAEs were lung infection (3.1%), dehydration (3.1%) and interstitial lung disease (3.1%). Most of the AEs were manageable and there were no treatment-related deaths reported during the study. Additional details are provided in the investigator brochure.

Preliminary data of clinical activity are summarized in Table 1.1.3-1. Nivolumab demonstrates single-agent activity in subjects with esophageal cancer (N = 64). Ten subjects had a partial response, 1 had a complete response, and 16 had stable disease under central review (Table 1.1.3-1). The ORR by central review was 17.2% and the mDOR was durable. The mOS was 10.78 months (95% CI: 7.39, 13.34) and the median PFS was 1.51 months (95% CI: 1.41, 2.83) in 64 evaluable subjects.

Table 1.1.3-1: Summary of Clinical Activity - ONO-4538-07				

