### **1.1.6 Rationale for Dose Selection of Nivolumab in Combination with Ipilimumab (Arm A) and Chemotherapy (Arm B) in First-line ESCC Subjects**

As described in Section 1.1.4, it may be beneficial to administer nivolumab in combination with ipilimumab in the treatment of ESCC, as it has demonstrated activity across multiple tumor types, including NSCLC and melanoma. Nivolumab 3 mg/kg Q2W in combination with ipilimumab 1 mg/kg Q6W was selected for Arm A, as it allows the study of clinical benefit of the addition of ipilimumab 1 mg/kg Q6W to nivolumab 3 mg/kg Q2W, which is the dose studied for the treatment of advanced line ESCC (see Section 1.1.3 for ONO-4538-07 results). Further, this nivolumab-ipilimumab combination regimen is being tested in first-line NSCLC subjects (CA209-227, including Squamous and non-Squamous) due to enhanced tolerability versus regimens using ipilimumab Q3W. Finally, weight based dosing is being used in the combination of nivolumab and ipilimumab, to be consistent with nivolumab-ipilimumab combination dosing in other tumor types, e.g. NSCLC.

Nivolumab 240 mg Q2W in combination with FP chemotherapy was selected for Arm B, as it is the flat dose equivalent to 3 mg/kg Q2W dosing that has been studied in advanced line ESCC (ONO-4538-07). Nivolumab 240 mg Q2W was selected based on clinical data and modeling and simulation approaches using population pharmacokinetic (PPK) and exposure-response analyses of data from studies in multiple tumor types (melanoma, NSCLC, and RCC) where body weight normalized dosing (mg/kg) has been used.

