#### 2 STUDY DESCRIPTION

# 2.1 Study Design

This is a randomized Phase 3 study of nivolumab plus ipilimumab or nivolumab combined with fluorouracil plus cisplatin compared with fluorouracil and cisplatin combination in adult ( $\geq$  18 years) male and female subjects with unresectable advanced, recurrent or metastatic ESCC.

[figure not shown]
After signing the informed consent form, and upon confirmation of the subject's eligibility, subjects with unresectable advanced, recurrent or metastatic ESCC will be randomized in a 1:1:1 ratio to one of the following open-label treatments:

- Nivolumab-plus-ipilimumab (N+I) arm: Subjects will receive treatment with nivolumab 3mg/kg as a 30-minute infusion every 2 weeks and ipilimumab as a 30-minute infusion 1mg/kg every 6 weeks.
- Nivolumab-plus-chemotherapy (N+C) arm: Subjects will receive treatment with nivolumab 240mg as a 30-minute infusion on Day 1 and Day 15, fluorouracil 800mg/m²/day as an IV continuous infusion on Day 1 through Day 5 (for 5 days), and cisplatin 80mg/m² as a 30 to 120-minute infusion on Day 1 of 4-week cycle.
- Chemotherapy (CT) arm: Subjects will receive treatment with fluorouracil 800mg/m²/day as an IV continuous infusion from Day 1 through Day 5 (for 5 days), and cisplatin 80mg/m² as a 30- to 120-minute infusion on Day 1 of 4-week cycle.

Treatment with nivolumab or nivolumab with ipilimumab will be given for up to 24 months in the absence of disease progression (PD) or unacceptable toxicity. Chemotherapy will be given as per the study dosing schedule until PD or unacceptable toxicity.

Baseline and all subsequent scans will be submitted to a BICR for analysis and archiving, once the subject is randomized and throughout the study period.

Figure 2.1-1: Study Scheme

\*Treatment with nivolumab or nivolumab + ipilimumab will be limited to 2 year maximum duration

This study will consist of 3 phases: screening, treatment, and follow-up:

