# 2.2 Treatment Assignment

After the subject's initial eligibility is established and informed consent has been obtained, the subject must be enrolled into the study by entering information into the IRT system to obtain the subject number. Every subject that signs the informed consent form must be assigned a subject number in the IRT system.

Once enrolled in the IRT, subjects that have met all eligibility criteria (including the required tumor tissue received and result obtained by the central laboratory and the pathology report approved by the investigator) will be ready to be randomized through the IRT.

Subjects meeting all eligibility criteria will be randomized in a 1:1:1 ratio to either the N+I arm, or the N+C arm, or the CT arm. Randomization will be stratified by the following factors:

- 1) PD-L1 status (≥ 1% vs. < 1% [including indeterminate])\*
- 2) Region (East Asia (Japan/Korea/Taiwan [J/K/T]) vs Rest of Asia vs rest of world [RoW])
- 3) ECOG performance status (0 vs. 1).
- 4) Number of organs with metastases ( $\leq 1 \text{ vs.} \geq 2$ )

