#### Main changes include

- Added analysis to evaluate relevant treatment effect between N+I vs. N+C for key efficacy endpoints in Section 8.
- Added PD-L1 by CPS and MSI analysis in Section 7.8.2.
- Add language in section 7.1 to handle the small stratum in the stratified analyses.

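### Can the N+I versus N+C comparison in SAP Section 8 speak to ipilimumab's contribution when the arms also differ by chemotherapy?

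*SAP*

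**What the plan says.** Section 8 of the SAP opens with a neutral aim: "In order to evaluate the treatment effect between two experiment arms of N+I and N+C". The SAP's document history for version 4.0 describes the addition in the same way: "Added analysis to evaluate relevant treatment effect between N+I vs. N+C for key efficacy endpoints in Section 8". The section heading and third sentence add the second purpose, the ipilimumab component: "These analyses will help to evaluate the contribution of ipilimumab component in the N+I regimen in the Summary of Clinical Efficacy (SCE"). The same sentence limits this to use "in the Summary of Clinical Efficacy (SCE) and Clinical Overview (CO) if applicable".

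The planned outputs are stratified Cox hazard ratios for OS and PFS with 95% confidence intervals, response-rate differences and odds ratios, overlaid Kaplan-Meier curves of all three arms, and differences in restricted mean survival time (RMST) for OS. They cover PD-L1 expressing, PD-L1 negative and all randomized subjects. No significance level is attached to any of them.

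SAP Section 2.2 has subjects "randomized in a 1:1:1 ratio to either the N+I arm, or the N+C arm, or the CT arm". Protocol Section 1.1.6, in its dose rationale for Arm A, says of the chosen regimen that "it allows the study of clinical benefit of the addition of ipilimumab 1 mg/kg Q6W to nivolumab 3 mg/kg Q2W".

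**The concern.** To isolate one component of a combination, one normally compares the combination with the same regimen without that component. Here the comparator does not just lack ipilimumab; it has fluorouracil and cisplatin in its place. The contrast therefore mixes what ipilimumab adds to nivolumab with what chemotherapy adds to nivolumab, and the trial estimates neither separately.

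The design makes this more pointed. SAP Section 5 assumes the same OS and PFS distributions for both experimental arms, so the planning value of the N+I versus N+C hazard ratio is 1. At that value the implied ipilimumab effect equals the unknown chemotherapy effect. An author of the Summary of Clinical Efficacy could take a neutral result as evidence that ipilimumab adds nothing, which would not follow.

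The nivolumab-alone study cited in Protocol Section 1.1.6 does not close the gap. According to Protocol Section 1.1.3, "nivolumab monotherapy 3 mg/kg IV every 2 weeks (Q2W) was conducted in subjects with esophageal cancer refractory or intolerant to standard therapies". It was also single-arm, so it cannot give the effect of adding chemotherapy to nivolumab in any population.

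**Working it through.** Section 8 states no figure to reproduce. The question is what the contrast can identify.

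**Arms (SAP Section 2.1)**

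| Arm | Nivolumab | Ipilimumab | Fluorouracil + cisplatin |
|---|---|---|---|
| N+I | 3 mg/kg every 2 weeks | 1 mg/kg every 6 weeks | no |
| N+C | 240 mg every 2 weeks | no | yes |
| CT | no | no | yes |

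N+I versus N+C exchanges ipilimumab for chemotherapy. N+C versus CT gives nivolumab added to chemotherapy. N+I versus CT compares whole regimens. None of the three gives ipilimumab added to nivolumab. The nivolumab dosing basis also differs; Protocol Section 1.1.6 treats the two as equivalent, and both calculations below rely on that because they use a single nivolumab-alone reference.

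**Hazard-ratio scale.** Let h = HR(N+I vs N+C) and c = HR(N+C vs nivolumab alone). Under proportional hazards, HR(N+I vs nivolumab alone) = h × c, so ipilimumab is beneficial exactly when c < 1/h:

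- h = 1.10: c < 1/1.10 = 0.91
- h = 1.25: c < 1/1.25 = 0.80
- h = 0.80: c < 1/0.80 = 1.25

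The documents give no value of c for this population. Taking c from 0.6 to 1.1 as an assumed range:

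| Observed h | c = 0.6 | c = 0.8 | c = 1.0 | c = 1.1 |
|---|---|---|---|---|
| 0.80 | 0.48 | 0.64 | 0.80 | 0.88 |
| 1.00 | 0.60 | 0.80 | 1.00 | 1.10 |
| 1.25 | 0.75 | 1.00 | 1.25 | 1.38 |

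If c ≤ 1 then h × c ≤ h, so h is an upper bound on the ipilimumab hazard ratio. A favourable h is then conservative support, while a neutral or unfavourable h settles nothing. This bound is only approximate here: the design assumes a delayed effect and a cure fraction, and Section 8 itself allows for OS curves of different shapes.

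**RMST scale.** At any one truncation time,

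RMST(N+I) − RMST(N+C) = [RMST(N+I) − RMST(N)] − [RMST(N+C) − RMST(N)],

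where N is nivolumab alone. This is ipilimumab gain minus chemotherapy gain, and it holds without proportional hazards. If the chemotherapy gain is zero or more, the planned RMST difference is a lower bound on the ipilimumab gain.

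**Nearest figures in the documents.** Protocol Table 1.1.8-1 sets the three regimens side by side in lung cancer (all comers):

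| | Nivolumab + chemotherapy | Nivolumab + ipilimumab | Nivolumab |
|---|---|---|---|
| ORR | 43% | 43% | 23% |
| Median PFS, months | 5.7 | 8.0 | 3.6 |
| 1-year OS | 71% | 76% | 73% |

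For response, the two combinations differ by 43 − 43 = 0 points, while nivolumab plus ipilimumab exceeds nivolumab alone by 43 − 23 = 20 points. Assuming exponential times, the crude c is 3.6/5.7 = 0.63 for PFS and ln(0.71)/ln(0.73) = 1.09 for OS. These are separate small cohorts in another tumour, and Protocol Section 1.1.5 gives different nivolumab doses in the chemotherapy cohorts. They supply no value for this trial; they show only that c can fall on either side of 1.

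**What depends on the answer.** The objectives in SAP Sections 3.1 to 3.3 do not include ipilimumab's contribution. The alpha-controlled procedure in SAP Section 7.5.1 contains only comparisons with CT.

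**The case for a change.** The best argument for amending the SAP is timing. SAP Section 9.1 and the version 4.0 history record that no within-trial analysis had been done when Section 8 was added. An assumption written down before results is more credible than one supplied afterwards, and the lung cancer figures show that it can matter by endpoint. One sentence would cost nothing and would bring the heading into line with the neutral wording of the document history.

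The identification point stands in full: the contrast informs the ipilimumab component only under assumptions about chemotherapy added to nivolumab and about nivolumab dosing, and Section 8 states neither. What does not follow is that the SAP is wrong. It does not say the contrast isolates or estimates the component; it says the contrast helps, and the RMST bound shows how. The population, estimator and interval of each planned output would be the same with or without the assumption. The caveat is needed where an inference about ipilimumab is drawn, and Section 8 places that in the Summary of Clinical Efficacy and the Clinical Overview. Those documents are not part of this plan and may carry their own caveats.

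**Conclusion.** No change is needed. Section 8 specifies a valid randomized, descriptive comparison of two regimens, and its statement about the ipilimumab component is modest enough to be true. The unstated assumption is a gap in interpretation that the authors of the summary documents can be expected to fill.

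Its size depends on the result. With an observed hazard ratio of 1.00, an assumed HR(N+C vs nivolumab alone) of 0.6 to 1.1 gives an implied ipilimumab hazard ratio of 0.60 to 1.10, so the direction is open. With an observed 0.80, the same range gives 0.48 to 0.88, so the direction is not in doubt. These figures are illustrative; they rest on proportional hazards and on equivalence of the two nivolumab dosing bases. The RMST bound needs only that equivalence and no survival loss from adding chemotherapy to nivolumab. Stating these assumptions in the SAP would leave every planned output, test and trial conclusion as it is.
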